Data Analysis: Data was analyzed using GraphPad Prism version 10.3.1 (GraphPad Software, San Diego, CA). A complete case analysis approach was used. Descriptive statistics and 95% confidence intervals were used to describe population characteristics. All data sets were analyzed for normality to evaluate if there were violations in the equal variances assumptions between groups. Nonparametric testing was used as necessary following the results of testing. Age data demonstrated normal distribution with comparable variance and was analyzed using an unpaired t-test. Length of stay (LOS) data demonstrated non-normal distribution and was analyzed using Mann-Whitney-U Rank sum test. Demographic characteristics were analyzed using Chi-Square (χ^2). To assess for within and between group differences, a two-way repeated measures analysis of variance (ANOVA) with post-hoc uncorrected Fisher's least significant difference (LSD) multiple comparison test was completed. Statistical significance was set at an alpha level of 0.05 for all statistical tests.

References:

1. BITS - Bioness [Internet]. [cited 2025 Nov 13]. Available from: <https://bionessmedical.com/bits/>
2. Bells Test – Strokengine [Internet]. [cited 2025 Nov 13]. Available from: <https://strokengine.ca/en/assessments/bells-test/>

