Official Title: Evaluation of Bioness Integrated Therapy System (BITS) Touch Screen Technology to
Improve Field Awareness

Clinical Trial Number: NCT04930822

Study Closeout: June 27, 2025

STUDY PROTOCOL AND STATISTICAL ANALYSIS PLAN

Methods

Research design: Unblinded randomized control trial

Patient Population/Enrollment Criteria: Individuals enrolled in this study must meet the following criteria:

1. Individuals enrolled in this study must meet the following criteria:
 - ii. Adults, 18 years or older who are able to provide consent or have Power of Attorney (POA) able to consent.
 - iii. Must have an acute or subacute (diagnosed within the last 3 months) neurological diagnosis with a visual field deficit as verified by occupational therapist via confrontation testing.
 - iv. Admitted into Gaylord Hospital, a long term acute care hospital
 - v. Demonstrate the ability to follow 1 step directions
 - vi. Demonstrate sufficient upper extremity strength (as deemed appropriate by occupational therapist) to utilize BITS touch screen technology
 - vii. Ability to tolerate at least 30 minutes of intervention at a seated wheelchair level.

1. Exclusion Criteria:

1. Severe cognitive impairments: Unable to follow one step directions, inability to communicate pain, or to stop intervention if needed
2. Quadriplegia
3. Previous significant visual impairment impacting visual fields or resulting in legal blindness in past medical history
4. Re-admitted to Acute Care and do not return within 1 week
5. Currently on a ventilator for respiratory support
6. Unstable vital signs or deemed inappropriate to participate in therapy per RN/MD
7. Uncontrolled or new (within 24 hours) arrhythmias.
8. Unresolved or new (within 24 hours) deep vein thrombosis.
9. Concurrent severe neurological pathology/disease or stroke within 72 hours.
10. Any reason the physician may deem as harmful to the participant to enroll or continue in the study.

A total of at least 30 adult Participants meeting these criteria will be included. This will include 15 participants in "A" Group and 15 participants in "B" Group. There will be no upper age limitation.

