Equipment and Intervention: Used for this study was the Bioness Integrated Therapy System (BITS[®]) (Valencia, CA) with 55-inch display.¹ As participants were consented and enrolled, they were alternately assigned to either the control group or the experimental group using the BITS. Over three-weeks, both groups received six, 20 minute long, vision-specific treatment sessions. The control group completed conventional table-top and pen and paper exercises, while the experimental group completed gamified, technology-assisted versions of similar exercises. Outside of these sessions, participants completed a standard rehabilitation regimen consisting of

three hours of daily comprehensive therapy (i.e., physical, occupational, speech, etc.) as prescribed by their treating physician.

Subject Assignment: Participants will be screened through an electronic report extracted from the electronic medical record. This will include all patients admitted under the stroke and traumatic brain injury (TBI) programs who have documentation supporting visual field impairments in the initial occupational therapy evaluation. Once they have been screened and all inclusion/exclusion criteria have been reviewed, patients will be consented to participate in the study and randomly assigned to "A" and "B" group in alternating fashion. If a participant exits the study before completion, their spot in the intervention will be replaced by a new participant.

Study Timeline: The enrollment period commences after the IRB has approved the study and the study initiation visit has been conducted. The enrollment and data collection periods are expected to last 12 months to obtain 30 participants. The goal is to have participants participate in scheduled occupational therapy sessions lasting a minimum of 20 but no more than 30 minutes for a total of six sessions focusing on vision therapy vs BITS training.

Outcome Measures and Data Collection: The primary outcome measures included the Bells Test, conducted by an occupational therapy practitioner involved in the study, and Kinetic Visual Field testing, conducted by a licensed neuro-optometrist.² Bells and Kinetic Visual Field Testing were completed at baseline and again following the six study sessions.

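### Exits are replaced, post-testing is described only after all six sessions, and only complete cases are analysed, so the comparison is of completers if leavers went untested

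*Combined protocol and SAP*

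**What the plan says.** Three rules bear on this point.

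- Methods, Subject Assignment: "If a participant exits the study before completion, their spot in the intervention will be replaced by a new participant". The text does not say whether the new participant takes the vacated arm or the next alternating slot.
- Methods, Outcome Measures and Data Collection: "Bells and Kinetic Visual Field Testing were completed at baseline and again following the six study sessions". No other post-test is described.
- Statistical Analysis, Data Analysis: "A complete case analysis approach was used". No reason, as-assigned set, imputation or sensitivity analysis accompanies it.

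The treatment course is "Over three-weeks, both groups received six, 20 minute long, vision-specific treatment sessions". The target is at least 30 participants, 15 per group. Two exclusion criteria can apply after enrolment: item 4, "Re-admitted to Acute Care and do not return within 1 week", and item 10, "Any reason the physician may deem as harmful to the participant to enroll or continue in the study".

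**The concern.** Patients in an acute or subacute phase of neurological illness may stop because they deteriorate, are discharged early or do not tolerate the tasks. All of these can be related to the outcome. If leavers have no post-test, a complete-case repeated measures ANOVA drops them, and what remains compares people who finished six sessions. That comparison is distorted when exit depends on outcome and the arms differ in how many leave or in which kind of patient leaves. The result would also apply only to finishers.

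Replacement makes this hard to see. The planned 15 per group can be reached whatever the attrition, so the analysed N says nothing about how many were assigned.

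**Working it through.** **1. What follows from the text.** A participant who exits is replaced. Post-tests are described only after six sessions. Only complete cases are analysed. If a leaver has no post-test, that person is outside the analysis and a newcomer fills the place. The step from leaving to having no post-test is an inference. So is counting patients who meet exclusion items 4 or 10 after assignment as replaced exits.

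**2. The plan's own figure.** 15 + 15 = 30, which agrees. The documents give no effect size, SD, power or exit rate, so neither the N nor any bias can be derived from them. The rest is illustration under stated assumptions.

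**3. What the analysed N hides.** To finish with 30 completers at exit rate d, about 30/(1 − d) must be assigned:

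- 5%: 30/0.95 = 31.6, so 32
- 10%: 30/0.90 = 33.3, so 34
- 20%: 30/0.80 = 37.5, so 38

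The analysed N is 30 each time.

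**4. Bias by hand.** Suppose leavers are g SD worse than completers. The completer mean then exceeds the mean of all assigned by d × g. With no true effect and the same g in both arms, the completer difference is g × (d1 − d2), in favour of the arm with more exits. For g of 0.5 and 1.0:

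- 20% v 20%: 0
- 20% v 10%: 0.05 and 0.10 SD
- 20% v 0%: 0.10 and 0.20 SD

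If poorer patients leave one arm and better patients the other, the difference is g × (d1 + d2). Even 10% v 10% then gives 0.10 and 0.20 SD. This is why type of exit matters as well as rate.

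**5. Simulation.** Assumptions: no true effect, 15 completers per arm, pre-post correlation 0.6, and logistic exit with poorer patients more likely to leave (log-odds slope 0.5, 1 or 2 per SD). The test is a t-test on change, which equals the group-by-time test with two time points. There were 20,000 trials per scenario; Monte Carlo error at a 5% rate is √(0.05 × 0.95/20,000) = 0.15 percentage points.

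| Exit depends on | Exit rates | Bias in SD, slopes 0.5 / 1 / 2 | Type I error |
|---|---|---|---|
| Change | 20% v 20% | 0.002 / 0.000 / −0.002 | 4.8 to 5.0% |
| Change | 20% v 10% | 0.039 / 0.078 / 0.105 | 5.1 / 5.9 / 6.5% |
| Change | 20% v 0% | 0.081 / 0.156 / 0.236 | 5.4 / 7.5 / 11.3% |
| Final score | 20% v 10% | 0.02 to 0.05 | 5.0 to 5.2% |
| Final score | 20% v 0% | 0.041 / 0.071 / 0.106 | 5.4 / 5.6 / 6.0% |

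Repeat runs agree within simulation error; the 20% v 10% case reaches 0.11 SD and 6.6%.

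**6. Does replacement itself bias the result?** Enrolling until there are 15 completers per arm gives 0.081 / 0.156 / 0.236 SD (change-driven, 20% v 0%). A large sample of completers with no replacement step gives 0.085 / 0.155 / 0.233. They are the same, so replacement conceals attrition but adds no bias.

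**7. Scale.** With 15 per arm, 80% power and two-sided 0.05 (the plan does not state sidedness), the noncentral t gives 1.060 SD of the change score. Multiplied by √(2 × (1 − 0.6)) = 0.894, that is 0.948 SD of the outcome. The largest bias in the table is 0.236/0.948, about a quarter of this.

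**The case against.** Complete-case analysis is a stated and legitimate rule, and exit counts belong in a results report rather than a plan. Both arms are inpatients of one hospital with the same session schedule, similar exercises and the same daily therapy, so a 20-point gap in exit is an extreme case. The more moderate 20% v 10% contrast barely moves the type I error. All of this stands, and it is why the size is put as modest and conditional. What it does not answer is that the plan offers no check on the assumption that exit is unrelated to outcome.

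Three stronger readings are tempting, and the documents support none of them.

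- A reader might infer that any exit necessarily turns the result into a completer comparison. The text says when tests were done; it does not say that leavers were left untested, or forbid testing them.
- A reader might infer that the trial's result is biased. No exit or replacement counts are given, and there may have been no exits.
- A reader might infer that replacement is itself a source of bias. Step 6 of the working shows that it is not.

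Nor does anything suggest that participants were analysed outside their assigned arm. Alternating assignment in an unblinded trial ("As participants were consented and enrolled, they were alternately assigned to either the control group or the experimental group using the BITS"; "Unblinded randomized control trial") is a separate limitation that an as-assigned analysis would not remove.

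**Conclusion.** The concern holds conditionally. If early leavers have no post-test, the plan as written yields a comparison of completers, and it contains nothing to test or disclose the effect of that. Bias requires exit to be related to outcome and to differ between arms in rate or type. Under the assumed rates and slopes it lies between about 0.02 and 0.24 SD, with type I error from about 5% to 11%, which is small beside what 15 per arm can detect. Those figures rest on assumed exit rates, a correlation of 0.6 and exit by poorer patients; they do not estimate anything in this trial. The change is worth making because it is cheap and standard, not because harm has been shown.

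**What to change.** **For the plan, or a repeat of the trial**

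1. Keep every assigned participant in the study for outcome assessment, and in the assigned arm.
2. Attempt the existing Bells and kinetic field post-tests at the end of the three-week window, or before discharge if that comes first, however many sessions were completed. Record the date.
3. Treat later enrolments as additional participants, not substitutes, and state which arm they enter.
4. Make the analysis of all assigned participants with available data primary. Keep the completer analysis and a simple sensitivity analysis for missing post-tests as secondary.

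Item 2 does most of the work, but only so far as the leavers reached are representative. In the change-driven 20% v 0% case at slope 1, bias falls from 0.155 to 0.056 SD if a random half is reached, but only to 0.116 if the better-changing half is. A mixed model using leavers' baselines alone is no substitute. It leaves 0.125 SD in that case, and raises bias from 0.068 to 0.112 when exit follows the final score.

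**For the data already collected (closeout June 27, 2025)**

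Report assigned, exited and replaced numbers by arm with reasons. Compare leavers' and completers' baselines. Label the result a completer comparison if anyone exited without a post-test. None of this recovers tests that were never done.

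**Cost**

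Prospectively: a few sentences of protocol and SAP text, and some time from the therapists and neuro-optometrist already involved. Test timing will vary in patients who may be recovering. Some leavers will be unreachable, and those reached may be the better ones. The estimate may be diluted by participants with fewer than six sessions.

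### The Data Analysis section is a post-closeout account of analyses already done and shows no outcome test or deciding contrast fixed before data were seen, so 0.05 is not shown to be any planned test's error rate

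*Combined protocol and SAP*

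**What the plan says.** The title block calls the document a study protocol and statistical analysis plan and gives "Study Closeout: June 27, 2025". Both entries in the reference list carry the access date "cited 2025 Nov 13".

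The Data Analysis section is entirely in the past tense. It opens with "Data was analyzed using GraphPad Prism version 10.3.1" and reports features of the collected data: "Age data demonstrated normal distribution with comparable variance and was analyzed using an unpaired t-test", and "Length of stay (LOS) data demonstrated non-normal distribution and was analyzed using Mann-Whitney-U Rank sum test".

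Three sentences bear on the outcomes:
- the scope of the distribution checks: "All data sets were analyzed for normality to evaluate if there were violations in the equal variances assumptions between groups";
- the rule for switching tests: "Nonparametric testing was used as necessary following the results of testing";
- the main method, for differences both within and between groups: "a two-way repeated measures analysis of variance (ANOVA) with post-hoc uncorrected Fisher's least significant difference (LSD) multiple comparison test was completed".

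The section sets 0.05 for every test. Under Outcome Measures and Data Collection, the Bells Test and Kinetic Visual Field testing are both named primary. No contrast is singled out for either.

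**The concern.** A reader of a document called a SAP will take the tests in it to have been fixed before the data were examined. This section cannot serve as evidence of that, because it describes completed work and observed distributions.

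The outcome text also leaves much open. It names no normality test, threshold or nonparametric alternative. The ANOVA yields a group effect, a time effect, an interaction and several uncorrected pairwise comparisons, and nothing says which of these answers the question about BITS. If any of them can be put forward, the chance that at least one falls below 0.05 with no true effect exceeds 5%. At stake is how much weight a p-value below 0.05 can bear when the trial is reported.

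**Working it through.** **Dates.** From 27 June 2025 to 13 November 2025 is 3 (rest of June) + 31 + 31 + 30 + 31 + 13 = 139 days. The dates place the last edit of this text after closeout. The tense and the reported distributions show that data had been examined by the time it was written.

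**The plan's own figure.** The 0.05 is a declared threshold, and no power or sample-size calculation is given, so there is no derived figure to reproduce.

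**What free choice could cost, for one outcome.** Inputs from the document: 15 per arm, one baseline and one follow-up measurement, 0.05 per test. Assumptions: normal data, two-sided tests (sidedness is not stated), pre-post correlation r = 0.7, no difference between arms and no change over time. There were 20,000 simulated trials. A false positive is counted when the smallest p in the set is below 0.05. With two time points, the group-by-time interaction F equals the square of the t statistic for the difference in mean change, so the first row is also the interaction test.

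| Tests available | At least one p < 0.05 |
|---|---|
| t-test on change, fixed | about 5% |
| t-test or Mann-Whitney on change | about 6% |
| t-test on change or on post-test | 9–10% |
| the same, plus Mann-Whitney on each | 10–11% |
| the same, plus group main effect (t-test on the pre/post mean) | 12–13% |
| the same, plus the two within-arm pre/post tests | about 18% |

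The ranges cover repeat runs. At r = 0.5 and r = 0.8 the set that includes the main effect gives about 12%, so r matters little.

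**The normality switch alone.** For a single two-sample comparison with 15 per arm, suppose a rule fixed in advance: Shapiro-Wilk at 0.05 in each arm, then t-test or Mann-Whitney. The error rate is 0.049 for normal data, 0.048 for lognormal data and 0.052 for a skewed 0–35 score with a ceiling. Taking the smaller of the two p-values instead gives 0.055, 0.060 and 0.063. Switching tests therefore costs about one percentage point at most. Most of the rise in the table comes from the unnamed contrast.

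**Pairwise comparisons.** A two-group, two-time layout has four natural LSD contrasts. If they were independent, the chance of at least one p below 0.05 would be 1 − 0.95^4 = 0.1855. For two primary instruments with one test each it would be 1 − 0.95^2 = 0.0975. Real contrasts and outcomes are correlated, so these are upper-end figures for those counts.

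**The case against.** Several points against the concern are sound.

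- The only data-driven choices that the section spells out are for age and length of stay. Neither is a primary outcome. The ANOVA is stated without reference to how the outcome data looked.
- The date of writing is not the date of deciding. The late access dates belong to a device page and a Bells Test page, not to any statistical choice. Future-tense wording in the enrolment, assignment and timeline text suggests that part of an earlier protocol survives, and an earlier analysis plan may exist. Title and signature pages are not in the text available, so the lack of a version date counts for nothing.
- A test chosen by a normality check is close to harmless if the rule is fixed beforehand, as the figures above show.

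A reader might infer that the text disproves pre-specification, or that the outcome method was picked with results and arm in view because the trial was unblinded. The documents support neither reading. They do not say who chose the outcome method or when, and they fail to show pre-specification rather than refute it. Nor does the document call its results confirmatory.

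What survives is narrower. The normality checks covered all data sets, the nonparametric option is open-ended, no deciding contrast is named, and the surviving future-tense text contains no analysis.

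**Conclusion.** The concern holds as a failure to show pre-specification. The document gives no outcome analysis fixed before data were seen, so its 0.05 level is not shown to be the false-positive rate of any single planned test. This limits what may be claimed and does not show any result to be false.

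On the stated assumptions, the illustrative error rate for one outcome runs from about 5% with a fixed contrast to 12–13% with free choice among between-arm analyses, and about 18% once within-arm tests count. It would be tempting to read these as upper limits. They are not: the list of tests is incomplete, and choices among outcome summaries, eyes and analysis sets are left out. The choice actually exercised cannot be known from the documents. A dated earlier plan naming the same method, outcome and contrast would restore pre-specification to that extent.

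**What to change.** In the Data Analysis section:

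1. Supply any dated earlier analysis plan and report its analysis first, or state that none exists.
2. Mark each outcome-analysis choice as planned before outcome data were accessed, or as post hoc. The cut-off should be first access to outcome data and not closeout, because in an unblinded trial a choice made before closeout may still have been made with data in view.
3. Keep the age and length-of-stay sentences as a record of what was done. For each primary outcome, report one stated between-arm contrast, the group-by-time interaction (the difference in change), with its 95% CI, whatever the normality tests show. Label it post hoc if it is chosen now. Do not base conclusions about BITS on within-arm or uncorrected LSD comparisons.
4. Label all remaining p-values exploratory, and note that a confidence interval from a post hoc model carries the same selection caveat.

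The cost is text edits and one analysis run. The downside is a weaker claim if no earlier plan can be produced.
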